#### Main Criteria for Evaluation and Analysis:

#### Primary variable:

ESS mean absolute change from baseline to the end of the 6-week treatment period will be analysed with an ANCOVA model, with the baseline ESS as a covariate, region and treatment as a factor. Missing data in the 6-week ESS evaluation will be considered as a treatment failure, that is imputing the missing ESS reduction as 0. Least-squared (LS) absolute mean changes will be presented by treatment group together with their corresponding 95% confidence interval. Paired-comparisons will be performed without any multiplicity adjustment.

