#### 11.1.1 Data Sets Analysed

The safety population (SAF) will be defined as all subjects who have received at least one dose of the study treatment.

The intent to treat population (ITT) will be defined as all subjects who have taken at least one dose of study treatment and who have available a post-baseline evaluation of the primary efficacy endpoint at screening/baseline and at week 6.

The per protocol population (PP) will be defined as all subjects in the FAS who do not experience a major protocol deviation.

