#### 11.1.3 Efficacy Analyses

# 11.1.4 Primary Efficacy Analyses

ESS mean absolute change from baseline to the end of the 6-week treatment period will be analysed with an ANCOVA model, with the baseline ESS as a covariate, region and treatment as a factor. Missing data in the 6-week ESS evaluation will be considered as a treatment failure, that is imputing the missing ESS reduction as 0. Least-squared (LS) absolute mean changes will be presented by treatment group together with their corresponding 95% confidence interval. Paired-comparisons will be performed without any multiplicity adjustment.

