# 11.5. Handling of dropouts or missing data

For the primary analysis ESS missing at 6-weeks will be inputed under the treatment failure approach.

As sensitivity analyses, a mixed-effect model with repeated measures (MMRM) approach will be used, under the missing at random framework carried out using an adequate contrast at Week 2 or Week 6, accordingly. The model will include fixed categorical effects of treatment group, visit and treatment-by-visit interaction as well as the continuous fixed covariates of mean baseline ESS. This MMRM model will be run with an unstructured correlation matrix to model the within-subject errors.

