9.4 Analysis sets Analysed for Efficacy

Primary Analysis, and sensitivity analysis as described above will be based in the ITT Population. In the MCP-Mod sensitivity analysis, only patients in the ITT with ESS evaluations at week 6 will be considered. Primary analysis will be repeated in the Per Protocol Population also which will be considered as a sensitivity analysis.

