10 STATISTICAL METHODOLOGY FOR EFFICACY ENDPOINTS

10.1 Primary Efficacy Analysis

ESS mean absolute change from baseline to the end of the 6-week treatment period will be analysed with an ANCOVA model, with the baseline ESS as a covariate, region and treatment as a factor. Least-squared (LS) absolute mean changes will be presented by treatment group along with their associated 95% CIs and 2sided p-values; these data will then provide estimated for the within arm change from baseline. The difference between each of the 3 dose arms and the placebo arms in Least-squared (LS) absolute mean changes will also be presented together with the corresponding 95% confidence interval and 2-sided p-value. These paired comparisons will be performed without any multiplicity adjustment. Also, the 4 degrees of freedom (DF) associated with the overall F-test for differences between the treatment arms will be decomposed using Type I sums of squares into three orthogonal single DF contrasts to estimate the linear, quadratic and cubic components of any potential dose response. Baseline data will be imputed with the baseline ESS average. Multiple Imputation Jumping to Reference method will be used to impute post-baseline data (see section 10.4.2 for further reference).

10.1.1 Sensitivity analyses missing reductions imputed to 0:

Same primary analysis will be repeated imputing post-baseline missing ESS evaluations to baseline data that is reduction equal to 0.

10.1.2 Sensitivity analyses MMRM Model:

A mixed-effect model with repeated measures (MMRM) approach will be used, under the missing at random framework carried out using an adequate contrast at Week 2 or Week 6, accordingly. The model will include fixed categorical effects of treatment group, region, visit and treatment-by-visit interaction as well as the continuous fixed covariates of mean baseline ESS. This MMRM model will be run with an unstructured correlation matrix to model the within subject errors. In this case missing values will not be imputed, since (MMRM) is handling missing data through the Maximum Likelihood estimation method.

Unstructured covariance matrix is assumed to explain within subject covariance in MMRM method in protecting the type I error rates. In the event if the assumption of unstructured covariance (UN) matrix results in non-convergence of the model, only then the following covariance structures will be considered in the order mentioned below.

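### Protocol and SAP specify different primary analyses (imputation of missing ESS, ITT definition, region factor), while SAP 1 and SAP 14 declare no change

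*SAP*

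**What the plan says.** **Protocol.** ITT is the main efficacy set (11.1). Section 11.1.1 defines it as dosed subjects "who have available a post-baseline evaluation of the primary efficacy endpoint at screening/baseline and at week 6". The primary analysis is an ANCOVA of the week-6 ESS change on baseline ESS, region and treatment. Section 11.1.4 adds: "Missing data in the 6-week ESS evaluation will be considered as a treatment failure, that is imputing the missing ESS reduction as 0". The Summary has the same rule, and 11.5 refers to it by its label: "For the primary analysis ESS missing at 6-weeks will be inputed under the treatment failure approach". Section 11.3 defines three regions: USA, Western Europe and Eastern Europe. The primary endpoint (6.2.1) covers both the within-group change and the difference from placebo.

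**SAP.** The ANCOVA has the same terms (10.1). Section 6 takes as ITT every randomised subject who was dosed, with no week-6 condition. Section 9.4 confirms that subjects without a week-6 score belong to this set, because only for MCP-Mod does it say that "only patients in the ITT with ESS evaluations at week 6 will be considered". For missing scores, "Multiple Imputation Jumping to Reference method will be used to impute post-baseline data"; 9.1 and 10.4.2 agree, and 9.1 puts the label 'treatment failure' on this method. The protocol's rule returns as sensitivity analysis 10.1.1: "Same primary analysis will be repeated imputing post-baseline missing ESS evaluations to baseline data that is reduction equal to 0". For missing baseline values, "Baseline data will be imputed with the baseline ESS average". Section 10.4.1 merges regions with fewer than 20 subjects and gives any site with 20 or more its own category in the region factor. Section 1 says that the SAP leaves the protocol's analysis as it is and sends deviations to Section 14. Section 14 reports none.

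**The concern.** The primary analysis of the primary endpoint should be the same in both documents, or the change should be declared. Here it is neither. The reported primary result would not be the one that the protocol describes, while the SAP states that nothing changed. The shared label makes the switch easy to miss.

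The protocol also conflicts with itself. Read as worded, its ITT contains only subjects with a week-6 ESS, so its own rule for a missing week-6 ESS has nobody to act on.

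The new method is also under-specified. SAP 9.1 and 10.1 refer to 10.4.2 for it, and 10.4.2 is one sentence without an imputation model, number of imputations, seed or variance method. SAP 9.2.1 carries the same imputation into the secondary ESS endpoints.

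**Working it through.** **Text comparison**

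- Imputation: zero reduction (Protocol Summary, 11.1.4, 11.5) against jump-to-reference multiple imputation (SAP 9.1, 10.1, 10.4.2). The SAP lists zero reduction separately as 10.1.1, so by its own account these are two analyses.
- Version: the SAP cites Amendment 03 (23 August 2017); the current protocol is Amendment 04 (7 November 2018). The Amendment 03 change table already gives zero reduction as the new primary text, so the version lag does not explain the difference.
- ITT: week-6 ESS required (Protocol 11.1.1) against not required (SAP 6). The Amendment 03 table makes ITT the main population but shows no change to its definition. Whether the difference predates the SAP cannot be told.
- Region: three regions (Protocol 11.3) against the merging and splitting rule of SAP 10.4.1. With 230 subjects at about 48 sites the average is 230/48 = 4.8 per site, so the site rule would act only where recruitment is very uneven.
- Baseline-mean imputation: the protocol is silent. It should rarely act, because baseline is the last value before randomisation (SAP 9) and entry requires a screening ESS.

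**Size of the effect**

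The plan gives no figure for this, so there is none to reproduce. Inputs from the documents: true difference 3.0, drop-out about 15%, 230 randomised. Assumptions: placebo improvement p, drop-out d1 on drug and d0 on placebo (m when equal), drop-out unrelated to outcome, all dosed subjects kept. Improvements are written as positive points.

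Placebo difference:
- Zero reduction: (1−d1)(p+3) − (1−d0)p
- Jump-to-reference using baseline only: 3(1−d1)
- Size of the gap: p × |d1−d0|

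1. Equal drop-out: both give 3(1−m), which is 2.85, 2.70 and 2.55 at 5%, 10% and 15%.
2. Within arm, equal drop-out: the rules differ by m × p. At 15% and p = 2, the drug arm gives 0.85 × 5 = 4.25 under zero reduction and 4.25 + 0.15 × 2 = 4.55 under jump-to-reference. The placebo arm gives 0.85 × 2 = 1.70 against 2.00. At p = 4 the drug arm gives 0.85 × 7 = 5.95 against 6.55.
3. Unequal drop-out, 20% drug and 10% placebo, p = 2: 0.80 × 5 − 0.90 × 2 = 2.20 against 3 × 0.80 = 2.40. With the rates swapped: 0.90 × 5 − 0.80 × 2 = 2.90 against 2.70.
4. Use of week-2 ESS: if jump-to-reference conditions on the week-2 score relative to the subject's own arm mean, the difference at 15% in both arms stays at 2.55. If week-6 values come from the placebo regression on week-2 ESS, it becomes 3(1−m) + m × b × (week-2 benefit), where b is the regression slope. With assumed b = 0.4 and benefit 1.5, this is 2.55 + 0.15 × 0.4 × 1.5 = 2.64. With b = 0.7 and benefit 3.0, it is 2.55 + 0.15 × 0.7 × 3.0 = 2.87 (rounded). Both assume that every drop-out has a week-2 score. If half do, the range is about 2.59 to 2.71.
5. Protocol 11.1.1 taken literally: the analysis uses observed week-6 scores and targets 3.00 instead of 2.55, with 0.15 × 230 = 34.5 subjects leaving the set.

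The missing share may be below 15%, because an early-termination ESS on days 22 to 45 can fill the week-6 slot (SAP 4.1).

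**The case against.** **Details are left to the SAP (Protocol 11.1).** This covers baseline-mean imputation, where the protocol is silent, and arguably the levels of the region factor, which 11.1.4 does not spell out. It does not cover replacing a stated primary imputation rule. In any case SAP 1 requires deviations to be listed in Section 14.

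**Both documents say treatment failure.** Protocol 11.1.4 defines that as zero reduction, and SAP 10.1.1 keeps zero reduction as a different analysis. The label does not reconcile them.

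**The ITT sentence in Protocol 11.1.1 is garbled, and SAP 6 gives the sensible reading.** This stands. The imputation rule shows that subjects without a week-6 score were meant to stay in. The contrast of 3.00 with 2.55 is therefore the cost of a literal reading, not the expected consequence.

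**Jump-to-reference is a defensible method.** Agreed. The point is the undeclared and incomplete switch.

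Three stronger readings are tempting and not supported:

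- That the sponsor can choose between the two results after unblinding. The SAP alone names one primary analysis, plans both imputations, and must be signed before database closure.
- That the switch necessarily favours the drug. The order reverses when drop-out is higher on placebo.
- That the placebo difference moves only at unequal drop-out. This depends on how week-2 ESS enters the imputation, which SAP 10.4.2 leaves open.

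**Conclusion.** The concern holds and must be fixed before unblinding. The protocol and the SAP differ on the primary imputation, the ITT definition and the make-up of the region factor, and the declarations in SAP 1 and SAP 14 are wrong. On imputation, Section 14 is wrong even against the protocol version that the SAP cites.

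The numerical effect is moderate and conditional. The within-arm change, which is part of the primary endpoint, shifts by m × p at any drop-out (0.30 points at 15% and p = 2). The placebo difference separates by p × |d1−d0| when drop-out is unequal. At equal drop-out it separates only if week-6 values are imputed from the placebo regression on week-2 ESS. The placebo improvement, the drop-out split, the week-2 slope and benefit, and drop-out unrelated to outcome are all assumptions; the documents give only the overall 15%.

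**What to change.** Before unblinding:

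1. **ITT.** Use the SAP 6 definition. Either correct Protocol 11.1.1 or declare in SAP 14 that SAP 6 replaces it.
2. **Primary imputation.** Name one. Either restore zero reduction as primary in SAP 9.1, 10.1 and 10.4.2, with jump-to-reference as the sensitivity analysis, or keep jump-to-reference and declare it as a change in SAP 14. Under either route:
   - complete SAP 10.4.2 with the imputation model (including how week-2 ESS is used), number of imputations, seed and variance method;
   - use 'treatment failure' only for zero reduction, which means editing SAP 9.1;
   - confirm that SAP 9.2.1 follows the chosen rule for the secondary ESS endpoints.
3. **Declaration.** Correct SAP 1, state which protocol version the SAP applies to, and replace the SAP 14 sentence with a full list from a line-by-line comparison with the current protocol. The list includes at least:
   - ITT definition, primary imputation, baseline-mean imputation and region pooling;
   - responder analysis: Chi-square or Fisher's exact test (Protocol 11.1.5) against logistic regression (SAP 10.2);
   - Per Protocol scope: primary and sensitivity analyses (Protocol 11.1.4) against the primary analysis only (SAP 9.4).

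Cost: document edits only, no new data, and both imputations are already planned. The SAP-only repair touches Sections 1, 9.1, 10.4.2 and 14, and also 10.1 and 10.1.1 if zero reduction is restored. Correcting the protocol text needs an amendment; the sponsor judges whether it is substantial and so needs ethics and authority approval (Protocol 10.2).

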10.1.3 Sensitivity analysis using MCP-Mod

This sensitivity analyses will be done for patients in the ITT population having non-missing ESS evaluation in the week 6.

MCP-Mod will be produced following the steps below, (see Pinheiro J 2014 (1) for reference):

- I. Candidate dose-response shapes
- II. Derive optimum contrast coefficients to maximize power to finding dose-response association
- III. Identify whether dose-response signal could be established
- IV. Model Selection

I. Candidate dose-response shapes

The three models detailed below will be considered in the dose-response evaluation.

- a. E_{max_1} ($D_{50}=0.2$): according to Thomas et al. Emax model can adequately describe the observed data in many situations. The Emax model dose-response curve is defined as:

$$R = E_0 + (D \times E_{max}) / (D + ED_{50})$$

where:

R = response

D = dose

E_0 = basal effect corresponding to the response when dose of drug is 0.

E_{max} = maximum effect attributable to the drug

ED_{50} = dose which produces half of the Emax

- b. Exponential ($\delta=1$):

$$R = E_0 + E_1 * (EXP(D/\delta) - 1)$$

E_0 = basal effect corresponding to the response when dose of drug is 0

E_1 = slope parameter for exponential model

D = dose

δ = parameter, controlling the convexity of the model

- c. Sigmoid Emax ($ED_{50}=1, H=8$):

[figure not shown]
E_0 = basal effect corresponding to the response when dose of drug is 0

E_{max} = maximum effect attributable to the drug

ED_{50} = dose which produces half of the Emax

H = Hill parameter, determining the steepness of the model at the ED_{50}

The following plot illustrates visually the shape of these three models used in the MCP part to test the dose-response signal:

II. Optimal Contrast identification

In order to obtain the vector of optimal coefficients \hat{c} for each dose-response signal contrast, the following equation will be maximized as proposed by Pinheiro, Bornkamp, Bretz (2006): $c'\mu/\sqrt{\sum c_i^2/n_i}$. The following steps will be performed for each curve (e.g. Emax₁):

1. A dataset with one single record and four variables μ_1, μ_2, μ_3 and μ_4 will be created where μ_1, μ_2, μ_3 and μ_4 are means for placebo, 0.5, 1, and 3 mg/d respectively compatible with the shape of the given curve (e.g. Emax₁).
2. The goal is to obtain the values c_1, c_2, c_3 and c_4 that maximize $(c'\mu)^2/(\sum c_i^2/n_i)$ where n_1, n_2, n_3 and n_4 are the sample sizes for placebo, 0.5, 1, and 3 mg/d respectively. To do so, the NLMIXED procedure will be applied on the above-mentioned one-record dataset to obtain the “maximum likelihood” parameters c_1, c_2, c_3 and c_4 using the following likelihood function:

$$ll = (\mu_1 * c_1 + \mu_2 * c_2 + \mu_3 * c_3 + \mu_4 * c_4) ** 2 / (c_1 ** 2 / n_1 + c_2 ** 2 / n_2 + c_3 ** 2 / n_3 + c_4 ** 2 / n_4);$$

There are infinite solutions to the above problem, so we will hold one coefficient to an arbitrary value (e.g. $c_1 = -10$).

3. Finally, the obtained coefficients will be normalized as follows (shown for c_1):

Sponsor BenevolentAI Bio
 Project Code ... BB-2001-201b

$$ncl=c1/(sqrt(c1**2 + c2**2 +c3**2 + c4**2));$$

For validation purposes, the obtained coefficients will be compared with the ones obtained using the dose-finding R package developed by te authors of MCP-Mod.

III. Dose Response Test

For each of the candidate models, dose-response association will be evaluated using the optimal coefficients identified in the previous step. These contrasts will be tested using the PROC GLIMMIX procedure at an one-sided alpha level of 0.025 and multiplicity adjusted p-values will be obtained through parametric resampling ESS mean absolute change from baseline to the end of the 6-week treatment period will be included in the model as dependent variable, dose as fixed factor and baseline ESS as covariate. SAS code like the code below will be used:

```
PROC GLIMMIX;
CLASS DOSES;
MODEL ESS = DOSES BASELINE /NOINT;
LSMEANS DOSES;
ESTIMATE "EMAX1"          DOSES &C11. &C12. &C13. &C14.,
        "EXPONENTIAL"    DOSES &C21. &C22. &C23. &C24.,
        "SIGMOID EMAX"    DOSES &C31. &C32. &C33. &C34.
        / UPPERTAILED ADJUST=SIMULATE (NSAMP=100000 SEED=1234) ;
RUN;
```

IV. Model Selection

The maximum contrast test method will be used to select the best model to be used in the Mod stage. The selected model will be fitted with PROC NLMIXED procedure using SAS code similar to the script below (shown for the Emax model only):

```
PROC NLMIXED;
BOUNDS S2>0, ED50 >0;
PARMS S2 BETA E0 EMAX ED50;
IF DOSE >0 THEN MEAN = E0+(EMAX*DOSE)/(ED50+DOSE) + BETA*BASELINE;
ELSE IF DOSE = 0 THEN MEAN= E0 + BETA*BASELINE;
MODEL ESS ~ NORMAL(MEAN, S2);
RUN;
```

A graph will be produced presenting the modelled dose-response curve; point estimate and 95% confidence limits will be displayed.

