5 SAMPLE SIZE AND POWER ESTIMATION

A total of 200 completed subjects will be evaluated for the study (50 completed subjects per treatment group, with expected early withdrawal rate of around 15%).

The assumptions used for the sample size calculation are a mean absolute change in the Epworth Sleepiness Scale (ESS) from baseline to the end of the 6-week treatment period of at least 3.0 points (minimum change considered as clinically relevant) and a standard deviation of 5.0 (based on a comparable study of Modafinil in a similar population recruited at one centre (3) which showed a standard deviation in the ESS between 3.5 at baseline and 4.8 at the end of the treatment period) and a reduction in ESS of 2.7 points for subjects treated with Modafinil.

The confirmation of the hypothesis of detecting a mean difference in ESS of 3.0 points vs. baseline requires a sample size of 25 subjects per group (intragroup $\Delta=3.0$; $SD=5.0$; two-side $\alpha=0.05$; $\beta=0.20$; power=80%; one-sample t-test).

The additional endpoint of showing a statistically significant difference of at least 3.0 points in ESS between Bavisant and placebo requires a sample size of 50 subjects per group (between treatment $\Delta=3.0$; $SD=5.0$; two-side $\alpha=0.05$; $\beta=0.20$; power=80%; two-sample equal-variance t-test).

The effect size of Bavisant in EDS is unknown and smaller changes in ESS may be clinically useful according to its profile, and higher variability is expected in this multicentre study; so the sample size of 200 completed subjects (50 per treatment group) is proposed in order to cover both the confirmation of an intragroup change of at least 3.0 points vs. baseline, and the between-group difference of at least 3.0 points change vs. placebo.

The Maintenance of Wakefulness Test (MWT) will be performed in a minimum of 20 subjects per group (80 overall) in order to be enough to show statistically significant differences if the expected MWT absolute change from baseline differs at least in one standard deviation (effect size = 1.0).

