9.1 Primary Endpoint for Efficacy

ESS mean absolute change from baseline to the end of the 6-week treatment period will be defined as the Total ESS score at visit 3 – Baseline ESS score. ESS questionnaire consists of 8 questions which subjects are asked to rate their usual chances of dozing off or falling asleep while engaged in eight different activities. The answers will be provided on a 4-point scale: 0=' would never doze', 1=' slight chance of dozing', 2=' moderate chance of dozing', or 3=' high chance of dozing'. Total ES is the sum of the entries for all of the 8 items-questions. If one or more item-scores are missing, it would not be imputed and this ESS total score will be considered invalid. When ESS was missing in some scheduled post-baseline visit (visit 2 or visit 3) any other ESS total score measured in whether an unscheduled visit or in the early termination visit will be considered according to the re-allocation windows rules presented in section 4.1. Remaining missing for baseline ESS will be imputed to the baseline average, and remaining post-baseline evaluations will be considered as treatment failure, a Multiple Imputation Jumping to Reference Approach will be used (see section 10.4.2 for reference). Negative absolute change will mean improvement.

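### MCP-Mod sensitivity analysis: no sum-to-zero condition on the coefficients, so the one-sided 2.5% level is not guaranteed, and the sign of the contrasts is left open

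*SAP*

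**What the plan says.** Protocol 11.1.4 lists MCP-Mod as sensitivity analysis b) and leaves the details of curve selection and validation to the SAP. SAP 10.1.3 then sets out these steps.

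- **Means.** Step II creates four values that "are means for placebo, 0.5, 1, and 3 mg/d respectively compatible with the shape of the given curve". The readable text gives no numbers and asks for no centring.
- **Criterion.** It first gives a signed criterion, c'μ/√Σ(cᵢ²/nᵢ), stating that "for each dose-response signal contrast, the following equation will be maximized as proposed by" the cited method paper. The function actually to be programmed is the square of this.
- **Side condition.** The only restriction on the coefficients is "so we will hold one coefficient to an arbitrary value", with c1 = −10 as the example. The result is then rescaled to unit length.
- **Validation.** The SAP says that "the obtained coefficients will be compared with the ones obtained using the dose-finding R package", and gives no action if they differ.
- **Test.** Step III uses "MODEL ESS = DOSES BASELINE /NOINT" with "UPPERTAILED ADJUST=SIMULATE (NSAMP=100000 SEED=1234", at a one-sided level of 0.025 adjusted over three shapes.
- **Direction.** SAP 9.1 defines change as visit 3 minus baseline and adds: "Negative absolute change will mean improvement".

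**The concern.** There are two separate points.

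**Level.** The criterion does not change when all coefficients are multiplied by a constant. Holding one of them therefore removes the scale and nothing else, and does not make the coefficients sum to zero. If they do not, the statistic responds to the average level of change and to the baseline slope as well as to differences between doses. Because the model has no intercept, any set of dose coefficients is estimable, so the software would run a non-contrast without warning.

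**Direction.** Squaring discards the sign. The sign then comes from an arbitrary held value, while the tail is fixed as upper and benefit is a negative change.

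In a trial described as dose-finding, this is the only dose-response test in the SAP with multiplicity-adjusted p-values. Step IV also uses the largest contrast statistic to choose the curve to be fitted.

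**Working it through.** **Inputs from the SAP.** 50 per arm, SD 5 and a 3-point effect (section 5); a baseline SD of 3.5, from the cited comparator study ("standard deviation in the ESS between 3.5 at baseline and 4.8 at the end of the treatment period"); one-sided 2.5%; shapes Emax (ED50 0.2), exponential (δ = 1) and sigmoid Emax (ED50 1, H = 8) (10.1.3).

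**Assumed, not in the documents.** Baseline mean 16 (range 14–18); placebo change E0; slope of change on baseline; means entered as E0 with a 3-point fall at 3 mg. In the table, E0 is both the entered placebo mean and the true common change.

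**1. The plan's own figure.** With coefficients that sum to zero, the flat-null rejection rate is 2.5–2.6% (10,000 trials per scenario; max-t critical value 2.29). The stated level is therefore attainable.

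**2. What the written rule gives.** By Cauchy–Schwarz, (c'μ)² ≤ Σ(cᵢ²/nᵢ)·Σ(nᵢμᵢ²), with equality when cᵢ ∝ nᵢμᵢ. Numerical maximisation with c1 = −10 agrees for all three shapes. For Emax, D/(D + 0.2) scaled to 1 at 3 mg is (0, 0.762, 0.889, 1).

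- E0 = −2: μ = (−2, −4.286, −4.667, −5), so c = (−0.241, −0.515, −0.561, −0.601), sum −1.92. The sums for exponential and sigmoid are −1.83 and −1.86.
- E0 = +0.5: the sums are 1.57, 0.53 and 0.90.
- E0 = 0: c1 drops out of c'μ but still adds 100/50 to the denominator. The criterion therefore rises with the scale of the other coefficients towards 50 × 9 × (0.762² + 0.889² + 1) ≈ 1066.8 and never reaches it. It is identical for both signs, so there is no finite maximum at c1 = −10.
- Centred μ: Emax (−0.846, 0.127, 0.289, 0.430), exponential (−0.337, −0.297, −0.229, 0.863), sigmoid (−0.454, −0.450, 0.150, 0.754). All sum to 0.

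**3. Effect on the level.** With no dose effect, every dose intercept equals α = E0 − slope × 16. Write S = Σcᵢ. The statistic has mean αS and variance 25 × [1/50 + (16S)²/Sxx], with Sxx = 196 × 3.5² = 2401. Referring αS/SE to a noncentral t on 195 df, at critical value 2.00 (E0 −2) or 2.17 (E0 +0.5), gives the Emax-only column. The last column is the simulated test over all three shapes.

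| E0 | slope | α | S | αS | SE | αS/SE | Emax only | three shapes |
|---|---|---|---|---|---|---|---|---|
| −2 | 0 | −2.0 | −1.92 | 3.84 | 3.21 | 1.19 | 21.2% | 22.4% |
| −2 | −0.3 | 2.8 | −1.92 | −5.37 | 3.21 | −1.67 | 0.0% | 0.0% |
| +0.5 | 0 | 0.5 | 1.57 | 0.78 | 2.66 | 0.30 | 3.1% | 4.7% |
| +0.5 | −0.3 | 5.3 | 1.57 | 8.32 | 2.66 | 3.13 | 83.1% | 84.7% |

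Over baseline means of 14–18, the first, third and fourth rows become 19–26%, 4–5% and about 85%. With baseline SD 3 and mean 16, the four rows are 17.5%, 0.0%, 4.5% and 73.4%. In the second row the 2.5% ceiling holds, but power for a 3-point benefit is only 0.3–1.0%.

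A second simulation fixed the entered E0 at −1 and varied the true common change (0 to −3) and slope (0 to −0.5). It gave 0% to 31%, and 2.7% when change and slope were both 0.

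**4. Direction, once the coefficients are contrasts.** Take centred means and c1 = −10. The placebo coefficient is negative for every shape, and reversing the sign of all entered means changes nothing. The flat-null error is 2.6%, so the level is right. Power with the upper tail:

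| | Emax | exponential | sigmoid |
|---|---|---|---|
| 3-point benefit, c1 = −10 | 0.0% | 0.0% | 0.0% |
| 3-point worsening, c1 = −10 | 87.0% | 91.2% | 90.8% |
| 3-point benefit, placebo coefficient positive | 85.6% | 90.9% | 90.5% |

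This reversal is not general when the means are uncentred. With E0 −2 and slope 0, benefit is detected in 49–72% of trials and worsening in 2–7%.

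**The case against.** The strongest reply is that the SAP names its coefficients contrasts throughout, and a contrast sums to zero by definition. On that view the gap lies in a worked recipe and not in the declared method. The coefficients are also to be checked against the method authors' own R package, and SAP section 2 puts all analyses under a quality check. A failed validation would normally be resolved. The plot of the three shapes could not be read in the copy reviewed and might show the placebo level. Both c1 = −10 and the SAS code are given only as examples. The error rates rest on assumed values, and the 84.7% case needs placebo means entered as a 0.5-point worsening together with a slope of −0.3.

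Some of this stands. The remark that no means are given applies only to the readable text, and if the plot carries values, the request to state them may be moot. The error rates show that the level is undetermined; they do not estimate this trial's risk. The two points also do not describe the same implementation: the general reversal of direction arises only once the coefficients are true contrasts.

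The rest does not remove the fault. The label does not alter the function to be programmed, and the plot is said only to illustrate shape. The R comparison has no acceptance rule and does not say which set of coefficients would be used.

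**Conclusion.** The concern holds. As written, step II yields coefficients proportional to nᵢμᵢ, and the one-sided 2.5% level follows only if the entered means have weighted mean zero, which the SAP does not require. Under the assumed baseline mean, placebo change and slope, flat-null rejection runs from 0.0% to 84.7%; centring restores 2.6%. Separately and conditionally, adding only the zero-sum condition while keeping c1 = −10 and the upper tail would leave a test with no power for benefit. Both corrections are needed.

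The reach is limited. This is a sensitivity analysis in ITT patients with a week 6 ESS, and no decision rule is attached to it. The primary ANCOVA, its polynomial contrasts and the Hill fit are untouched. It should be fixed, but it does not threaten the primary result.

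**What to change.** In SAP 10.1.3:

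1. State the assumed μ for each shape, and require c1 + c2 + c3 + c4 = 0. Equivalently, replace the numerical search with the closed form cᵢ ∝ nᵢ(μᵢ − μ̄), where μ̄ is the n-weighted mean.
2. Set the sign so that c'μ > 0 for the assumed falling ESS curve. The placebo coefficient is then positive and UPPERTAILED can stay. Keeping placebo negative and using LOWERTAILED is equivalent.
3. Require the coefficients to match the R package in sign and magnitude before the test is run.

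The cost is a few lines of SAP text and code before unblinding. No data or patients are affected.
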